Comparison of traditional diarrhoea measurement methods with microbiological indicators:

Protocol

[name], [name], [name], [name], [name], [name]

Executive Summary

In slums and informal settlements, 16% of all infant deaths are attributable to diarrhoeal disease, an entirely preventable cause of death. This burden of diarrhoeal disease is due in large part to lack of access to water, sanitation, and hygiene (WASH) systems that can prevent the spread of faecal pathogens. A key challenge for WASH provision is the difficulty in evaluating and monitoring the effectiveness of WASH systems. Evaluations of WASH interventions typically use diarrhoea incidence as a primary endpoint, measured by self-reported diarrhoea and often in under-fives, which serves as a proxy for enteric infection. However, there is a notable lack of evidence on how accurate self-reported diarrhoea incidence is as a marker for enteric infection. Self-report may be subject to recall and ascertainment biases, along with the act of being observed or subject to intervention possibly leading to differential reporting.

This study will investigate the 'diagnostic accuracy' of diarrhoea self-report for enteric infection by evaluating against the sampling of stool for analysis of faecal pathogens and biomarkers of infection. Not only does this provide a means to estimate the association between infection and reported diarrhoea, but it also allows for measurement of asymptomatic infection – which is still a target of WASH interventions. This study will randomise participants into one of two diarrhoea measurement arms for surveys: a basic survey for infant diarrhoea (similar to DHS) and an enhanced survey for infant diarrhoea (using tools such as the Bristol stool scale); and subsequently randomly selecting a subgroup from each arm to undergo faecal stool testing of infants. The primary outcomes will be the positive and negative predictive values of self-reported diarrhoea for enteric infection. As a secondary outcome we will examine the types of pathogen present. We would conduct a survey at baseline in February/March, a time with low diarrhoeal disease incidence; and June/July, a time with high diarrhoeal disease incidence - to account for seasonality, and to measure variation in respondent fatigue for the various methods. This research will take place in the Cox's Bazar refugee camp, which may also allow for analysis of the burden of carriage of disease which is not endemic to Bangladesh.

Background

Diarrhoea is one of the two most common causes of death and morbidity in children under five (Kaseebaum, 2016) (Lilford et al, 2017). Upgrades to water and sanitation facilities are a key strategy to deal with this problem, for which proper monitoring and evaluation is needed to determine which interventions are working for a context, and which are not. A primary endpoint for determining the effectiveness of water and sanitation of infections is diarrhoea prevalence, both a primary endpoint in itself, in that diarrhoea is a substantial cause of morbidity and mortality in infants residing in areas with poor access to water and sanitation services; and a proxy marker for enteric infection, which in itself is may be flawed due to possibly high rates of asymptomatic carriage. As we describe, however, there are substantial concerns over the measurement of diarrhoea. We hypothesise that measurement issues may have contributed to the variable and often unexpectedly null results of recent studies, especially cluster trials, of various interventions, and are conducting this study to determine the effect of these biases (Luby et al, 2018) (Null et al, 2018).

The presence of diarrhoea is generally assessed by questionnaire, asking whether a child has experienced three or more loose or liquid stools in a given period, typically in the past 24 hours or two weeks. However, despite the importance of this, there are few studies on the validity of this tool - with the few studies that have been conducted suggesting that current methods are not performing well (Schmidt et al, 2011). Longer recall periods, such as two weeks, are subject to fallible memory and recall bias. Shorter periods are additionally affected by other biases. For example, the more frequently a person is asked about diarrhoea, the less likely they are to report diarrhoea (Clasen et al, 2014). It has also been found that diarrhoea rates are subject to Hawthorne effects, differential behaviour due to knowledge of being observed (Leonard et al, 2006). Additionally, while loose and liquid stool are generally defined by taking the shape a container, judgement on the specifics of this may also vary between individuals. These biases may be reduced by a more comprehensive survey including pictures, such as the Bristol Stool Chart (Lewis et al, 1997). Likewise, stunting, the other outcome often used in studies of WASH interventions, is a commonly used outcome measure in studies of gastrointestinal health, however the multiple causes of growth retardation and time required for it to manifest mean it is unlikely to be sensitive to intervention in anything but the longest duration studies.

Aims and Objectives

Despite the importance of the topic there have been few studies on the accuracy and reliability of diarrhoea measurement methods. The aim of this study it to evaluate the accuracy of reported diarrhoea rates as a proxy for enteric infection, using both a standard and enhanced reporting method for diarrhoea, with sub-aims:

- To assess the relative differences between "standard" and "enhanced" questionnaires.
- To analyse the pathogenic profile of stool samples.
- Determining carriage of pathogens from Myanmar to Bangladesh.

Design and Methodology

Sampling

The study will follow a two arm RCT design in which 400 households will be recruited through random household sampling in both the formal and informal refugee camps in Cox's Bazar (Fig.1). The random household sampling will use an EPI sampling method, in which a series of random angles and distances from a pre-determined central point (e.g. a water tap) will be generated, selecting households closest to the mapped location. This list will be generated at the beginning of the data collection period, with households randomly assigned to each research assistant.

Inclusion and exclusion criteria

Inclusion and exclusion criteria for the study is as follows:

Inclusion	Exclusion
Household has at least one child under the age of five	Household is expecting to relocate/resettle/repatriate in the next 6 months
Household has at least one adult over the age of 18	
Household consents to study	

Recruitment

Households will be initially contacted by research assistants travelling door to door who will ask to speak with an adult in the household. The study will be explained through the use of the participant information sheet, with households meeting inclusion criteria being consented and enrolled in the study. As part of consenting, GPS coordinates, name, and mobile phone number will be recorded. Households who do not consent will not have mobile phone numbers recorded, but will have GPS coordinates recorded to ensure that the house is not approached again. Mobile phone numbers and GPS coordinates will be recorded separately from data in a log book, and linked to individual household identifiers which will be recorded on the survey form.

Diarrhoea survey

Households will be randomised in a 1:1 ratio into the basic survey, a survey asking if a child had diarrhoea and dysentery in the past two weeks, based on DHS survey measures; and the enhanced survey, based on qualified stool charts (of which images will be displayed on the tablet during surveying), proxies for diarrhoea (such as oral intake), and measures of waterwashed diseases. All households will also be administered a basic demographic survey with questions on education, health, living environment, and WASH usage. If a household reports dysentery, they will be given the information of a local clinic for treatment. All surveys will be translated into Rohingya, and back translated into English – with translation following WHO guidelines: aiming for the simplest translation with the conceptual equivalent, targeted toward the target audience or Rohingya refugees, many of whom are illiterate with a low level of education. This will be done through consultation with Rohingya community members to ensure proper translation.

Data collection will take place at two time points: February/March and June/July. Research assistants will collect data through the use of ODK on an Android tablet. Data will be stored on the tablets and uploaded to Warwick servers at the end of each day, when research assistants return to the base office. Data will be additionally verified daily.

Stool sampling

Within each arm at each time point, 20 households reporting diarrhoea, and 20 not reporting diarrhoea, will be selected to have the oldest infant under 5 undergo stool testing - a total of 80 households at each time point, 160 in total. The first 20 households reporting diarrhoea and not reporting diarrhoea in each arm will be selected and asked if they are willing to provide stool samples. A WhatsApp group will be created for the research assistants to determine when 20 consenting households have been reached in each arm. The consenting households will be given a stool collection container once the survey has been administered, which will be collected the following day. All stool containers will be labelled with a barcode which will be scanned by the research assistant using a tablet, to link the stools sample with the survey. Stool will be collected by the carer, and tested for the presence of predetermined organisms which are endemic to the Rohingya population, along with a small number of select pathogens that are not endemic (Table 1); and for the presence of biological markers of infection: calprotectin and lactoferrin. This will be done through the use of polymerase chain reaction analysis (PCR) at the laboratory at the ICDDR,B in Dhaka, Bangladesh. Stool will also be tested for blood using a faecal hemooccult test.

Туре	Species	Carriage period (adults)	Carriage period (children)
Bacteria	Shiga toxin-producing Escherichia	17-18 days (1)	35-69 days (2)
	Enteropathogenic Escherichia coli	ND	20—36 days (2)
	Enterotoxigenic Escherichia Coli	ND	<5 days (2)
	Enteroinvasive Escherichia Coli	ND	ND
	Enterohemorrhagic Escherichia Coli	ND	2-62 days (2)
	Salmonella typhi	12-25 days (3)	Varies (2)
	Salmonella paratyphi	28-55 days (4)	~30 days (2)
	Campylobacter	14-21 days (5)	Up to 6 weeks (5)
	Shigella	~28 days (6)	1-10 days (6)
	Cholera	~2 days (7)	~4 days (7)
	C. difficile	6-57 days (8)	6-57 days (8)
	C. perfringens	ND	ND
	Acinetobacter	7-11 days (9)	ND
Protozoa	Entamoeba histolytica	ND	ND
	Cryptosporidium	~8 days (10)	~8 days (10)
	Cyclospora	5-13 days (11)	22-23 days (11)
	Giardia	2-6 weeks (12)	~6 months (13)
Helminth	Ancylostoma duodenale	1-2 years (14)	ND
	Ascaris lumbricoides	Years (15)	Years (15)
Viruses	Rota-virus	Up to 35 days (16)	4-57 days (2)
	Hepatitis A	~21 days (17)	Up to 21 days (12)
	Hepatitis E	3-4 weeks (18)	ND
	Norovirus	ND	8-60 days (19)
	Human Caliciviruses	~14 days (20)	~12 days (20)
	Adenovirus	ND	8-23 days (20)
	Astrovirus	ND	1-10 days (20)
Fungi	Enterocytozoon	18-38 days (21)	9-40 days (22)

Informed consent

All respondents will be consented in the Rohingya language and given a demographic and behaviour survey at the first time point. All questionnaires and surveys will be translated into Rohingya and back translated into English, with all data collection will be completed by Rohingya research assistants.

Data analysis

Data will be analysed using Stata version 15. The following analyses will be conducted

- Incidence rate ratios and associated 95% confidence intervals comparing diarrhoea and dysentery incidence between:
 - o Enhanced and basic surveys
 - o Survey method and stool analysis method
- Positive predictive value and associated 95% confidence interval of reported diarrhoea for the presence of enteric pathogens
- The association between diarrhoea presence and other potential markers of enteric infection such as MUAC and water-related diseases, measured for example by Jaccard's index
- A logistic regression of diarrhoea prevalence on demographic and health variables to examine association.

All missing data will be reported and assumed to be missing at random. The sample sizes proposed here would give us power to estimate the self-reported diarrhoea rate in each arm to a 95% confidence interval of approximately ±4 percentage points, assuming a point prevalence of 10%. We would also be able to estimate the positive and negative predictive values to approximately ±7 percentage points assuming values of 90%.

Data Management

This study will produce survey data from the diarrhoea prevalence survey and results from labs studies of stool samples. Field survey data will be collected by tablet device using ODK. These data will contain identifiable information about the participants and so will be classified as 'reserved'. We will use survey software approved by the University of Warwick that abides by GCRF standards. The tablet devices will be locked by code and the field workers will have responsibility for managing the device. Completed survey forms are automatically encrypted and no longer accessible from the tablet, they are uploaded to the server and deleted when a connection is available. Lab results will be collated digitally and linked to survey participants by a unique identifier – which are also considered 'reserved'. They will be incorporated into a primary database. Data will be reviewed daily for quality. All data will be encrypted using AES-256 encryption and stored on University of Warwick servers. The data management plan for this project follows the data management plan for the NIHR health in slums project.

The data will be fully anonymised and made available publicly along with the publication planned for this work.

Ethics and Consent

Ethical approval will be obtained from the University of Warwick and a local Bangladeshi ethics board. Rohingya community groups will also be consulted in survey design to ensure that no social harm is caused.

Written consent will be obtained from the adult in the household being interviewed using an informed consent sheet in Rohingya, administered by Rohingya research assistants. The assistants will read the form to participants in the case of illiteracy. Participants have the option to withdraw participation at any time

Compensation

Compensation will not be offered as this is not anticipated to place a large time burden on participants.

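### The stool work-up has no measure of diarrhoea or visible blood, so infected non-reporters cannot be called asymptomatic and the survey-versus-stool incidence ratios lack a stool-side counterpart

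*Protocol*

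**What the plan says.** The Executive Summary gives as a benefit of stool testing that "it also allows for measurement of asymptomatic infection". The Background says that the investigators "are conducting this study to determine the effect of these biases", meaning the biases that affect reported diarrhoea.

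Stool sampling describes what is measured on the specimen. "Stool will be collected by the carer, and tested for the presence of predetermined organisms" (the Table 1 panel), and it is also tested "for the presence of biological markers of infection: calprotectin and lactoferrin". For blood, "Stool will also be tested for blood using a faecal hemooccult test". At handling, the only recording described is the barcode: "All stool containers will be labelled with a barcode which will be scanned by the research assistant using a tablet".

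Data analysis lists incidence rate ratios "comparing diarrhoea and dysentery incidence between" two pairs: the enhanced and basic surveys, and the survey method and the stool analysis method.

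In the sample survey (Appendix 3), stool appearance enters only through the carer's memory of the past two weeks. The basic arm has one yes/no item on loose stools and one on blood. The enhanced arm has a chart-aided item, followed by timing, number and duration. The chart belongs to the enhanced survey, "of which images will be displayed on the tablet during surveying".

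**The concern.** To call an infection asymptomatic, one must know the child's symptoms. Here the carer's report is the only source for them, and its accuracy is what the study sets out to test. Using it to define the asymptomatic group is circular, because a child with a positive stool and no report may be a carrier or may have had diarrhoea that went unreported.

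The planned ratio of diarrhoea incidence by survey against stool analysis has a gap of the same kind. Detecting an organism or an inflammatory marker is not detecting diarrhoea, so the stool side has no diarrhoea count to enter. For dysentery, the nearest stool measure is occult blood in one specimen, set against a carer's recollection of blood over two weeks. The two differ in what they detect and in the period they cover.

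At stake are a secondary claim about asymptomatic infection and two listed comparisons. If the label stands, a figure for infection among non-reporters could be published as a carriage rate when an unknown part of it is under-reporting.

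**Working it through.** **1. The plan's own precision figures.** Inputs are from Data analysis, Sampling, Diarrhoea survey and Stool sampling: 400 households randomised 1:1, so 200 per arm; reported prevalence 10%; predictive values 90%; 20 reporters and 20 non-reporters per arm per time point, so 20 × 2 × 2 = 80 of each. The half-width is 1.96 × √(p(1−p)/n).
- Rate per arm: 1.96 × √(0.10 × 0.90/200) = 4.16 points (stated: about 4).
- Predictive values: 1.96 × √(0.90 × 0.10/80) = 6.57 points (stated: about 7, which holds with both arms and both rounds pooled).

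Both reproduce, and neither depends on stool appearance.

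**2. Where symptom information comes from.**

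| Source | What it gives | Shows diarrhoea? |
|---|---|---|
| Basic survey | Carer's two-week recall, yes/no | By report only |
| Enhanced survey | Carer's two-week recall with chart | By report only |
| Organism panel | Infection | No |
| Calprotectin, lactoferrin | Markers of infection | No |
| Occult test | Blood, including blood not visible | No |
| Barcode scan | Link to the survey | No |

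**3. How much the label could hide, from the plan's inputs.** From the plan: reporting R = 0.10 and NPV = 0.90, so 0.10 × 80 = 8 infected among 80 tested non-reporters. Assumed, because the documents give no value: report specificity 1, and infection in 90% of true diarrhoea cases (which agrees with a PPV of 90%). Report sensitivity Se is varied.
- True diarrhoea: D = R/Se.
- Unreported cases: D(1−Se).
- Share of infected non-reporters who are unreported cases: 0.9 × D(1−Se) / [(1−R)(1−NPV)].

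At Se = 0.8, D = 0.125 and unreported cases are 0.025. The share is 0.0225/0.09 = 25%, or 2 of the 8.

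| Se | Share | Of 8 |
|---|---|---|
| 1.0 | 0% | 0 |
| 0.9 | 11% | 0.9 |
| 0.8 | 25% | 2.0 |
| 0.7 | 43% | 3.4 |
| 0.6 | 67% | 5.3 |
| 0.5 | 100% | 8.0 |

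With infection in 70% of true cases, the share runs from 0% to 78% over the same range. The planned data look the same in every row.

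**4. A second set of assumptions, none from the documents.** True two-week diarrhoea D of 12–20%, Se of 40–80%, specificity 98%, infection in 70% of true cases and in a fraction i of 10–50% of other children. Let u = D(1−Se)/(1−[D·Se + 0.02(1−D)]). The share is 0.7u/(0.7u + i(1−u)).
- Central case (15%, 60%, 30%): u = 0.06/0.893 = 0.067; share = 0.0470/(0.0470 + 0.2798) = 14%.
- Lowest (12%, 80%, 50%): 4%. Highest (20%, 40%, 10%): 52%.

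**5. What grading the stool could show.** If 0 of 80 non-reporter stools were loose, the exact 95% upper limit would be 1 − 0.025^(1/80) = 4.5%, for loose stool on the sampling day. It does not bound unreported episodes over two weeks. In the central case of step 4, 6.7% of non-reporters had an unreported episode, or 5.4 of 80. If episodes last 2, 3 or 5 of the 14 days (assumed), the chance of seeing no loose stool at all is (1 − 0.067 × d/14)^80, which is about 46%, 31% or 14%.

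**The case against.** The strongest reply is that no stated aim fails. The aim is the accuracy of reported diarrhoea as a proxy for enteric infection, and the primary outcomes are its positive and negative predictive values. A proxy that disagrees with infection is a poor proxy whether the cause is misreporting or carriage. Asymptomatic infection is offered as an added benefit and appears in neither the listed aims nor the listed analyses. All of this stands, and it limits the point to a label, two comparisons and a missing recording step.

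A reader might infer that the study cannot address reporting bias at all. The protocol does not support that: the 1:1 randomised comparison of questionnaires estimates the relative difference in reporting, and two survey rounds are meant to show respondent fatigue. What is unavailable is the absolute amount of under- or over-reporting.

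A reader might also infer that setting occult blood against reported dysentery must look like under-reporting. That is not established. Detecting unseen blood pushes one way, and episodes resolved before the sample push the other. The pairing itself is inferred, since Data analysis does not name the stool measure for dysentery.

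It is equally tempting to reserve 'asymptomatic' for non-reporters with a formed stool. That repeats the error, because a child with an unreported episode ten days earlier would also have a formed stool.

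Two practical objections stand. Grading stools with the chart in front of basic-arm carers could sensitise them before the second round and blur the randomised contrast. Also, laboratory and stool-collection forms are not shown, so the absence of grading is established only for the protocol text and sample survey.

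**Conclusion.** The point holds in limited form. As written, stool testing measures infection among children without reported diarrhoea, and the Executive Summary overstates this as asymptomatic infection. The survey-versus-stool ratio for diarrhoea has no diarrhoea measure on the stool side. For dysentery, the only stool blood measure is not comparable with two-week recall of blood. These last two conclusions rest on the text alone.

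The size of the possible mislabelling is unknown. It is 0% to 100% of infected non-reporters under the plan's 10% and 90% with assumed sensitivity from 1.0 down to 0.5, and 4% to 52% under the second set of assumptions. These ranges show what the data cannot distinguish; they do not estimate the error.

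The primary predictive values, their stated precision and the randomised questionnaire comparison are unaffected. The change is worth making because it is cheap and because appearance that is not recorded at collection cannot be reliably recovered at analysis.

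**What to change.** 1. **Executive Summary and reporting.** Call the estimate 'infection without reported diarrhoea', including for non-reporters whose collected stool is formed.
2. **Stool sampling.** In both arms, have the assistant record two items for each collected stool: the consistency grade on the chart already on the tablet, and visible blood yes/no. Do this out of the carer's sight, for example at the base office, so that basic-arm households are not sensitised before round two.
3. **Data analysis.** Replace the survey-versus-stool incidence ratios for diarrhoea and dysentery with reported diarrhoea against detected infection, cross-tabulated descriptively by observed loose or formed stool. Compare reported blood with visible blood and state the difference in time window. Keep occult blood as a marker of infection or inflammation.

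The cost is two tablet fields and about a minute per stool for the 160 planned stools, with no extra staff. The limitation is that one stool reflects only the sampling day, so grading is a partial check and can neither confirm nor exclude an episode within the two weeks. Items 1 and 3 remain necessary even if grading is declined; the parts of item 3 that use observed appearance would then fall away.

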
Has this child had 3 or more loose or watery stools any day in the past 2 weeks?	Yes	No
Has this child had blood in their stool in the past 2 weeks?	Yes	No

If yes to either, did you seek treatment for either of these?	Yes	No	
	lf yes, where?		

Enhanced Survey (50% of respondants)

IDENTIFY OLDEST CHILD UNDER 5												
Mid-Upper Arm Circumference			cm									
*SHOW AMSTERDAM	Consistency	А	В	С	D			_				
CHART*Has the child had any of these stools in the past 2 weeks	Colour	1	2	3	4	5	6					
How long ago?	1		2			3		4	5	6	7	Other:
How many times on the worst day?	1		2			3		4	5	6	7	Other:
How many days did it last?	1		2			3		4	5	6	7	Other:

References

- 1. Vonberg, Ralf P., et al. "Duration of Fecal Shedding of Shiga Toxin–Producing Escherichia Coli O104:H4 in Patients Infected During the 2011 Outbreak in Germany: A Multicenter Study." *Clinical Infectious Diseases*, vol. 56, no. 8, 2013, pp. 1132–1140., doi:10.1093/cid/cis1218.
- 2. ECDC. Systematic Review on the Incubation and Infectiousness/Shedding Period of Communicable Diseases in Children. 2016, Systematic Review on the Incubation and Infectiousness/Shedding Period of Communicable Diseases in Children, ecdc.europa.eu/sites/portal/files/media/en/publications/Publications/systematic-review-incubation-period-shedding-children.pdf.
- 3. Murase, T, et al. "Fecal Excretion of Salmonella Enterica Serovar Typhimurium Following a Food-Borne Outbreak." *JOURNAL OF CLINICAL MICROBIOLOGY*, vol. 38, no. 9, 2000.
- 4. Gunn, John S., et al. "Salmonella Chronic Carriage: Epidemiology, Diagnosis, and Gallbladder Persistence." *Trends in Microbiology*, vol. 22, no. 11, 2014, pp. 648–655., doi:10.1016/j.tim.2014.06.007.
- 5. Janssen, R., et al. "Host-Pathogen Interactions in Campylobacter Infections: the Host Perspective." *Clinical Microbiology Reviews*, vol. 21, no. 3, 2008, pp. 505–518., doi:10.1128/cmr.00055-07.
- 6. South Australia Health. "Shigella Infection Including Symptoms, Treatment and Prevention." SA Health, 2018, www.sahealth.sa.gov.au/wps/wcm/connect/public+content/sa+health+internet/health+topics/health+conditions+prevention+and+treatment/infe ctious+diseases/shigella+infection/shigella+infection+-+including+symptoms+treatment+and+prevention.
- 7. Weil, Ana A., et al. "Bacterial Shedding in Household Contacts of Cholera Patients in Dhaka, Bangladesh." *The American Journal of Tropical Medicine and Hygiene*, vol. 91, no. 4, 2014, pp. 738–742., doi:10.4269/ajtmh.14-0095.

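### The quota of 20 diarrhoea reporters per arm per round equals the number expected at the plan's own 10% prevalence, so the 80 reporter stools behind the ±7-point PPV precision are not secured

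*Protocol*

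**What the plan says.** - Size and allocation (Sampling; Diarrhoea survey): "The study will follow a two arm RCT design in which 400 households will be recruited" and "Households will be randomised in a 1:1 ratio into the basic survey", the other half receiving the enhanced survey. That is 200 households per arm.
- Stool quota (Stool sampling): "Within each arm at each time point, 20 households reporting diarrhoea, and 20 not reporting diarrhoea, will be selected", giving "a total of 80 households at each time point, 160 in total". Over both arms and rounds this is 80 reporters and 80 non-reporters. The field team is to "determine when 20 consenting households have been reached in each arm", so the quota counts households that agree to give stool.
- Planning prevalence (Data analysis): the precision of the self-reported rate is worked out "assuming a point prevalence of 10" per cent. One figure serves both arms and both rounds. The same paragraph gives about ±7 points for the predictive values at an assumed 90%.
- Timing (Executive Summary): "a survey at baseline in February/March, a time with low diarrhoeal disease incidence". Round 2 is in the high season.
- Not given: a season-specific prevalence, a stool consent or return rate, an allowance for loss by round 2, or a rule for a cell that does not reach 20.

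**The concern.** A quota set at the expected number of eligible households will be missed about half the time before anyone refuses. Because each cell stops at 20, a surplus in one cell cannot make up a deficit in another, so the expected total lies below 80 even under ideal conditions. PPV is a primary outcome and reporters are its only denominator. Round 1 is placed where reporters should be scarcest, and the two rounds exist partly to account for seasonality, so the thinnest cells would be those the seasonal comparison needs. A shortfall in round 1 cannot be repaired afterwards under the present wording.

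**Working it through.** **1. The plan's own figures.** Half-width = 1.96 × √(p(1−p)/n).
- Self-reported rate per arm: p = 0.10, n = 200 gives 1.96 × √(0.09/200) = ±4.2 points. This matches the stated ±4 and confirms 200 per arm.
- PPV at 0.90: n = 80 gives ±6.6; n = 40 (one arm, both rounds) gives ±9.3; n = 20 (one cell) gives ±13.1. The stated ±7 is therefore reproduced only with both arms and both rounds pooled. A half-width of ±7.0 needs 71 reporters.

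**2. Chance of filling a cell.** Let X ~ Binomial(200, prevalence × return), with the four cells treated as independent. Return means consent and delivery of a stool. Only the 10% comes from the protocol; every other rate is assumed.
- 10%, full return: mean 20; P(X ≥ 20) = 0.53 for one cell, 0.53² ≈ 0.29 for both arms in a round, 0.08 for all four.
- 10%, 90% return: mean 18, P = 0.34 per cell. A 10% loss of households by round 2 (180 per arm) with full return also gives mean 18 and P = 0.34.
- 10%, 80% return: mean 16, P = 0.18 per cell, 0.001 for all four.
- Low season 7%, full return: mean 14, P = 0.07. Low season 5%: mean 10, P = 0.003.

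**3. Expected reporter stools and pooled PPV precision.** The yield per cell is E[min(X, 20)]. At 10% with full return it is 18.3, so 4 × 18.3 ≈ 73. The last column is the exact probability that the sum of the four capped counts reaches 71.

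| Low / high season | Return | Expected stools (of 80) | Pooled half-width | P(at least 71) |
|---|---|---|---|---|
| 10% / 10% | 100% | 73 | ±6.9 | 0.74 |
| 10% / 10% | 90% | 69 | ±7.1 | 0.41 |
| 10% / 10% | 80% | 63 | ±7.4 | 0.12 |
| 7% / 13% | 100% | 67 | ±7.2 | 0.27 |
| 5% / 15% | 100% | 60 | ±7.6 | 0.01 |
| 5% / 15% | 80% | 55 | ±7.9 | <0.001 |
| 5% / 10% | 100% | 57 | ±7.8 | <0.01 |
| 5% / 10% | 80% | 47 | ±8.5 | <0.001 |

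At 5% a round 1 cell holds on average 10 of 20 stools with full return, and 8 of 20 with 80% return.

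**4. NPV.** At 10% each arm has about 180 non-reporters per round for a quota of 20, so the NPV denominator is safe.

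**5. What a carry-forward gains.** With 5%/15% and 80% return, an arm collects about 8 stools in round 1 and leaves 12 tests unused. Round 2 then has room for 32 and expects 24. The total is about 2 × (8 + 24) = 64, or ±7.4 instead of ±7.9. With 5%/10% there is little surplus to use: at full return at most 2 × (10 + 20) = 60, or ±7.6 instead of ±7.8.

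**The case against.** The case for leaving the plan alone has real weight.

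- The expected count at 10% is exactly 20, and the protocol says only approximately ±7. At 10% with full return about 73 stools give ±6.9, at least 71 are reached with probability 0.74, and at least 62 (±7.5) with probability 0.98. The 0.08 chance that all four cells fill does not measure the loss of ±7, which does not need four full cells. This stands.
- The wider half-widths rest on return and seasonal rates that appear nowhere in the protocol. This also stands; they show a range and are not predictions.
- The 10% is called a point prevalence, while the basic survey asks "Has this child had 3 or more loose or watery stools any day in the past 2 weeks". Two-week prevalence cannot be lower than point prevalence in the same children, and at 15% a cell fills with probability 0.985. But the protocol attaches the 10% to the self-reported rate that the survey measures, so using it here is fair.
- Refusers are passed over until 20 agree, and households expecting to relocate within six months are excluded. Both help, but neither is a numerical margin: with 20 reporters expected, there is on average nobody left to replace a refuser.

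A reader might infer that the quota cannot be met, or that the ±7 is lost. The protocol's figures do not support either: at 10% with full return the pooled precision is roughly met. A reader might also blame the shortfall for per-arm half-widths of about ±11. Most of that gap comes from splitting the arms, which gives ±9.3 even with full quotas.

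**Conclusion.** The concern holds as one of feasibility; the stated ±4 and ±7 are arithmetically sound. The quota has no margin, and 80 reporter stools (160 in all) is a size the design is unlikely to deliver: an 8% chance under the most favourable reading of the 10%, with 73 expected. The effect on pooled PPV precision is modest: none to speak of at 10% with full return, about 0.1 to 0.4 points beyond ±7 at an assumed 80–90% return, and about 0.6 to 1.5 points beyond it with an assumed 5% low-season rate and 10–15% in the high season. The heavier loss is in the round 1 cells, about half filled in the 5% scenarios. These results assume independent households and cells and a Wald interval at 90%. A true two-week prevalence well above 10% in both rounds would largely remove the problem; a low-season rate below 10% makes a round 1 shortfall the expected outcome.

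**What to change.** In Stool sampling, make 20 reporters per arm per round a target. Where round 1 falls short, offer the unused reporter tests to additional round 2 reporters in the same arm, within a fixed ceiling on total tests. Set that ceiling by reconciling the 160 stools planned in this section with the 120 laboratory tests in Appendix 2: at 129 USD each, the 40 unbudgeted tests come to 5,160 USD. If 120 is the true limit, an assumed even split gives 60 reporters and ±7.6 before any shortfall.

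Report PPV by round as well as pooled, because the carry-forward tilts the pooled estimate toward the high season.

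In Data analysis, restate the expected number of reporter stools and the PPV half-width over a stated range of season-specific prevalence and return rate (for example 5–15% and 70–100%). Say that ±7 applies only with both arms and both rounds pooled, and that it is ±9.3 per arm with full quotas.

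The cost is protocol wording, a slightly wider stated precision and the tilt just noted. No extra households are needed and the 160 stools are not exceeded. The gain depends on a high-season surplus, so the carry-forward does not replace the restated precision. The changes need to be in place before round 1 begins.
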